Study Visits will be conducted in outpatient research facilities associated with the UCSF Women's Health Clinical Research Center at [name] on the Mt. Zion campus, where two side-by-side office/exam rooms are equipped with all equipment needed to collect study measurements, or at [name], where coordinators will bring equipment needed for measurements to a rented private office.

D.6.1 Telephone Screening

Women who respond to study advertisements and notices by calling the study phone number will be provided with a general overview of the study and, if still interested, will complete a brief telephone survey to determine initial eligibility (age, severity of OAB, current and past OAB treatment, exclusionary conditions, availability during the study time period, and willingness to participate). Eligible respondents will be invited to attend a clinic screening visit and will be asked to bring all medications to the visit.

D.6.2 Screening Visit

At the screening visit, the study will be explained in detail, and informed consent will be obtained. Candidate participants will be told that this is a randomized trial of two different forms of relaxation therapy, slow-paced respiration and relaxing music-listening, for treatment of overactive bladder syndrome. They will complete questionnaires assessing demographics, medical history, surgical and gynecological history, medications, alcohol and tobacco use, and OAB symptoms. They will be shown the list of medications that they will need to avoid for the duration of the study. Height, weight, blood pressure, heart and respiratory rate will be measured.

Women will provide a clean-catch urine sample for assessment of urinary tract infection of hematuria, as well as to rule out pregnancy.

If eligible to continue, participants will be given a demo RESPeRATE run-in device and taught how to use it. At the screening visit, the participant will open the box containing the device, sensor strap, earphones, and batteries. After brief instruction (<5 minutes), the research assistant will assist the participant in correctly starting and using the device, answering any questions and making sure the participant is comfortable with device use. The participant will be instructed to place the belt-like elastic strap respiratory sensor around the upper chest over clothing, place the headphones on the ears, and breathe normally until the device recognizes her normal respiratory rate and begins to play background music. Each participant will then be asked to use their device to listen to relaxing music for at least 15 minutes per day at home during a 7-day run-in period.

Each participant will be given a 3-day voiding diary and instructions on using it to record all voiding and incontinence episodes for 3 days during the run-in period and indicate whether episodes were accompanied by a sensation of urgency. Each participant will also be asked to wear a wrist actigraph during the same 3-day period that they complete their voiding diary.

D.6.3 Run-in period

Because previous studies of RESPeRATE for other indications have shown that efficacy improves with adherence,^{57,60} all women will complete a 7-day run-in period between the screening and baseline visits in which they will demonstrate willingness to adhere to home RESPeRATE practice. For the run-in, women will be given a demo RESPeRATE run-in device that plays relaxing, non-rhythmic background music but does not pace their breathing. The music played by the demo run-in RESPeRATE devices will be similar but not completely identical to the music played by the regular RESPeRATE control devices that serve as the main control intervention for the study. Like the regular RESPeRATE control device, the demo RESPeRATE control device will automatically collect data on: a) time, date, and number of sessions in which it was used; b) duration of time for each session; c) average and range of respiratory rate during each session; and d) data quality (i.e., percent time that breathing was detected by the sensor). Women will be told to use their run-in RESPeRATE devices for at least 15 minutes each day during the run-in period, while sitting quietly and alone in a comfortable location, and avoiding listening to other music, watch TV, read, sleep, or perform any other distracting activity. For at least 3 days during the run-in period, women will also complete daily voiding diaries, which will be used to further assess women's compliance and to collect data on baseline severity of overactive bladder symptoms. Women will also be asked to wear a wrist actigraph while they complete their voiding diaries, push a button on the actigraph to indicate when they go to bed and when they get up each night, and complete a simple sleep diary over this same 3-day period.

D.6.4 Baseline/Randomization Visit

A baseline visit will be scheduled one to two weeks after the screening visit and completion of the run-in procedures. Participants will return with their completed voiding diary, the demo RESPeRATE run-in device, and the wrist actigraph and sleep diary. Diary data will be abstracted, and data from the run-in device and the actigraph will be downloaded. Those who are non-adherent to RESPeRATE practice or the diary will not be eligible to continue. Blood pressure, heart rate, and respiratory rate will be re-measured; participants who have a blood pressure <100/60 will also be ineligible to continue. If the demo RESPeRATE device indicates

home practice for at least 12 minutes on each of at least 6 days, the voiding diary is completed correctly on at least 3 days, and the diary reveals an average of at least 3 voiding or incontinence episodes per day associated with at least moderate urgency, and the participant meets other eligibility criteria and agrees to enroll in the study, she will be eligible for randomization to a regular active or control RESPeRATE device. Immediately following proof of eligibility, the study coordinator will randomize the participant, using the next sequential randomization envelope.

Following randomization, instruction in use of the active or control RESPeRATE device will be reviewed, and the participant will be asked to use the device for at least 15 minutes per day at home. The participant will be given the study phone number and instructed to call study staff for any questions or problems with the devices. Participants will be given a pamphlet providing brief information about usual care behavioral self-management of overactive bladder symptoms. Participants will be reminded not to take any medications known to affect overactive bladder symptoms during the treatment period.

Participants will also undergo non-invasive measurement of resting heart rate variability and pre-ejection period using the BIOPAC MP150 monitoring device at this visit (if they are randomized). They will complete questionnaires assessing condition-specific quality of life and anxiety and perceived stress symptoms.

D.6.5 Follow-up Visit (1 week)

After one week of treatment, participants will return to the clinic for early follow-up, bringing their RESPeRATE active or control devices. Downloaded RESPeRATE device data will be securely transferred to the study database. The study coordinator will review adherence with use of the active or control device, assess for side effects of treatment, and answer any questions. For safety monitoring, blood pressure, heart rate, and respiratory rate will be reassessed by study staff. Adverse events will be recorded on standardized forms. Each participant will also be given a new, blank voiding diary to complete for 3 days before her 6-week visit.

D.6.6 Follow-up Visit (6 weeks)

After 6 weeks of treatment, women will return to the clinic for follow-up for assessment of adherence, side effects, and concurrent medications, and to address any questions. They will return their 2nd completed voiding diary, in which they will have recorded all voiding and incontinence episodes over a 3-day period and indicated whether these episodes were associated with no, mild, moderate, or severe urgency. Data from RESPeRATE devices will be downloaded before the device is returned to the participant. Blood pressure, heart rate, and respiratory rate will be measured by study staff. Adverse events will be recorded on standardized forms. Participants will complete the same self-administered questionnaires about condition-specific quality of life and anxiety and stress given at baseline visit.

D.6.7 Follow-up Phone Call (9 weeks)

After 9 weeks of treatment, the study coordinator will contact participants by telephone to review adherence with use of the RESPeRATE device, assess for side effects, and answer any questions. At the participant's request, or if there is a safety concern, this visit may also be conducted in person. Participants will be reminded that to start completing their next voiding diary at least 3 days before their 12-week visit, and to wear

the wrist actigraph and complete their sleep diary during this same 3-day period. They will be reminded to bring their completed voiding diary, their RESPeRATE device, and their actigraph and sleep diary with them to that 12-week visit.

D.6.8 12-Week Visit

The final clinic visit will take place approximately 12 weeks after screening or at the time a participant decides to discontinue participation in the trial. Participants will return their third completed voiding diary, the RESPeRATE device, and the wrist actigraph and sleep diary. Participants will complete the same self-administered questionnaires that were given at the baseline and 6-week visits. They will also complete a close-out questionnaire about their satisfaction with the study interventions and procedures. Physical exam measures of blood pressure, heart rate, and respiratory rate will be repeated. Participants will also undergo repeat assessment of heart rate variability and impedance cardiography. Participants will receive instructions and materials for completing and returning the 24-week mail-in voiding diary and questionnaire packet.

D.6.9 24-Week Mail-In

Twelve weeks after returning their guided-breathing devices, women will complete a final voiding diary and set of questionnaires and mail it back to study staff, using a pre-addressed, pre-stamped envelope.

D.6.10 Time commitment

Telephone screening will require approximately 15 minutes. The screening clinic visit will require up to one and a half hours. The baseline clinic visit will require approximately two hours. The 6-week follow-up visit will require one and a half hours. The final (12-week) visit will require approximately two hours. The one-week and 8-week follow-up telephone calls will each require between 5 and 15 minutes. The total estimated time required for study visits is therefore 7 and a half hours, including 7 and hours of clinic visit time, and approximately one half hour of telephone time.

Additionally, participants must practice either slow-paced respiration or music-listening using their RESPeRATE devices for at least 15 minutes per day for 12 weeks, for a total of 21 hours of home RESPeRATE practice time. They must complete voiding diaries at four timepoints in the study (baseline, 6 weeks, 12 weeks, and 24 weeks), adding another 15 minutes at each of these timepoints. They must also complete a mail-in questionnaire packet at 24 weeks, adding another 30 minutes at this timepoint. The total estimated time required of participants at home is therefore 22 and a half hours. In summary, this 12-week study will require a total of 30 hours of participants' time, including 7 and a half hours of visit time, and 22 and a half hours of home time.

D.7 Adherence, Discontinuation, and Reimbursement

D.7.1 Overview

Every effort will be made to assure that participants adhere to the protocol and use the study interventions regularly. Participant contact information including address, phone number(s), fax number(s), and email

address will be obtained. We will also request contact information for two family members or friends who will be able to locate the participant. The study team will encourage retention by educating participants about the importance of the study, maintaining a friendly and efficient clinical center environment, and encouraging excellent staff-participant rapport. All identifying information will be kept confidential, appropriately secured and destroyed at the end of the trial.

D.7.2 Adherence to interventions

Adherence to study interventions will be assessed using data automatically collected by the RESPeRATE device and down-loaded at baseline, 1 week, 6 weeks, and 12 weeks. All participants will be encouraged to use the device as recommended for at least 15 minutes per day. Study staff will ascertain reasons for non-adherence and attempt to help participants find ways to improve adherence. However, participants who are non-adherent with study interventions will still be urged to attend all study visits and complete all study measurements as planned.

D.7.3 Adherence to study visits

All participants will be urged to attend all study visits and complete all study measurements as planned. However, participants can discontinue participation in the study at any time. Participants who miss a visit will be contacted by the study coordinator to reschedule the visit and to provide assistance in completing the visit. Participants who state that they no longer desire to participate in the trial will be asked to undergo final study measurements and complete a close-out questionnaire if possible.

D.7.4 Discontinuation of interventions

The study interventions will be discontinued in women with average blood pressure <90/50 or in those with blood pressure <100/60 as well as symptoms suggestive of hypotension such as dizziness. If possible, the final outcome measurements will be obtained in all participants who discontinue the intervention.

D.7.5 Participant reimbursement

Each participant will receive a \$25 gift card at the Baseline Visit and at the Week 6 Visit, a \$50 gift card after the Week 12 Visit, and a \$20 gift card after returning their mail-in packet at 24 weeks. Participants will therefore receive a total of \$120 in gift cards of their choice for their participation in the study. We will also provide parking voucher stickers for participants who wish to park in the UCSF Women's Health Clinical Research Center garage for their study visits.

D.8 Potential Risks and Safety Monitoring

D.8.1 Potential risks of study procedures

- A. Paced respiration: RESPeRATE is a commercially-available guided-breathing device (Costco, Amazon) that is FDA-approved for treatment of mild hypertension and widely used without a prescription. Risk to participants from use of RESPeRATE is minimal; in clinical trials that included over 492 participants, no side effects were reported. Additionally, our research team observed no side effects in our other randomized trial of 120 women with menopausal hot flashes treated with slow paced respiration. The effect of RESPeRATE on blood pressure decreases with lower baseline blood pressure such that it does not lower blood pressure in persons with baseline less than about 120 mmHg systolic.
- B. Music-listening: There are no known risks to participants associated with use of the RESPeRATE control device for music-listening. Although the music-listening control is designed to be relaxing and pleasant, it is possible that participants randomized to the control group may find this music to be unappealing or irritating.
- C. Questionnaires and diaries: Although the information participants provide on data collection forms and diaries is confidential, some participants may feel embarrassed at having to answer questions, especially those related to incontinence symptoms or depression and anxiety symptoms. Completion of diaries and questionnaires will involve slight inconvenience in time and effort.
- D. Physical exam measurements: There are no direct risks associated with undergoing measurement of height, weight, blood pressure, and heart rate at study visits, although some participants may experience this as inconvenient or unpleasant.
- E. Heart rate variability and impedance cardiography: Heart rate variability and cardiac impedance measurements will be obtained using a non-invasive BIOPAC MP150 electronic monitoring system. The only adverse effect that may result from these measurements is mild skin irritation at the site of the ECG or cardiac impedance electrodes, which generally disappears within 24 hours of removing the electrodes. Although noninvasive, measurement of heart rate variability and cardiac impedance may be experienced by participants as inconvenient or mildly unpleasant. Women will need to lift their shirts (but not remove their brassieres or underwear) for placement of the electrode sensors. They will also need to complete two brief computer-based tasks (approximately 5 minutes in duration each) that may be perceived as psychologically stressful while undergoing Biopac measurements.
- F. Computer-based concentration task: Participants will perform two types of brief, computer-based mental concentration tasks while undergoing heart rate variability and cardiac impedance measurements, including a visual attention and tracking task directed at assessing vagal withdrawal and a navigation task designed to assess sympathetic reactivity. Some participants may perceive these tasks to be stressful or annoying.
- G. Wrist actigraphy: There is no risk of injury from the wrist actigraph device to measure sleep activity though participants may find it mildly inconvenient to wear a wrist device for 3 days. It is possible that the strap of the actigraph wrist watch device may leave a small area of red skin or irritation which is usually painless and resolves within a few days.

D.8.2 Protections against risks

Women with low blood pressure (<100/60) at the screening or baseline visit will be excluded from the study. Participants will undergo repeat blood pressure measurement at each follow-up clinic visit (1 week, 6 weeks, and 12 weeks) and will be instructed to come to the study clinic to have their blood pressure re-measured if they develop dizziness, fatigue, or other symptoms suggestive of orthostasis. Use of RESPeRATE will be discontinued in participants with blood pressure <90/50, or in those with blood pressure <100/60 and symptoms consistent with hypotension.

Staff will be trained to be courteous and discrete when administering questionnaires, obtaining physical exam measurements, and assessing heart rate variability and impedance cardiography, and to follow-up with referrals to appropriate medical personnel when measurements are outside allowable ranges. Participants will be told that they can ask to pause or discontinue measurements if they become uncomfortable.

Participants who report an allergy or sensitivity to adhesives can decline to undergo heart rate variability or impedance cardiography measurements. Study staff will be trained to remove the EKG electrodes and tape in ways that minimize skin irritation or reaction. Participants with an allergy to metal can wear the wrist actigraph monitor over their sleeve or use a wrist sports sweat band to protect their skin. They can also decline to undergo wrist actigraphy measurements as a non-essential study procedure.

D.8.3 Adverse event monitoring

At each phone and in-person contact, participants will also be asked about any negative changes in their health, which will be recorded as adverse events or serious adverse events on standardized forms. An adverse event will be defined as any undesirable sign, symptom, or medical condition that occurs after starting therapy, whether considered related to the study intervention or not. Medical conditions or diseases present before starting the intervention will only be considered adverse events if they worsen after starting the therapy. According to standard practice, adverse events will be classified as mild, moderate, or severe. Adverse event forms will also record whether the event resolved or continues.

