After sensing the participant's normal respiratory pattern, the active device will begin to play a distinct musical tone to prompt inspiration and a second tone to prompt expiration. The device will first synchronize its tones to the user's spontaneous respiratory pattern, and then gradually increase the timing and duration of its tones to guide the user in slowing her respiratory rate and prolonging her expiratory phase. The participant will be instructed to simply try to match her inspiration and expiration to the tones. Participants will be asked to use the RESPeRATE device for at least 15 minutes per day at home while sitting quietly and alone in a comfortable location, not listening to other music, watching television, reading, sleeping, or performing any other distracting activity.

During practice sessions, the active device will automatically collect data on: a) the time, date, and number of sessions in which it was used; b) duration of time for each practice session; c) average and range of respiratory rate; d) data quality (i.e., percent time that breathing was detected by the sensor), e) amount of time

that the participant succeeds in slowing respiration to less than 10 BPM in each session, and f) the percentage of time that the participant's breathing pattern follows the device's musical tones. Participants will be instructed to use RESPeRATE for at least 15 minutes per day for a total of 12 weeks.

D.4.3 Control intervention

Participants who are randomized to the control group will use a control RESPeRATE device that does not pace respiration, but plays relaxing, non-rhythmic music while monitoring participants' spontaneous breathing rate at home. RESPeRATE devices can be re-programmed by research staff to be either active or control devices using software provided by Intercure, Ltd., and research staff will re-program devices as needed at participants' baseline visits. The control device will look exactly like the active RESPeRATE device, except that the device will not play musical tones synchronized to inspiration and expiration, but will play quiet, non-rhythmic music while monitoring spontaneous breathing.

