- A. Heart rate variability: Heart rate variability (i.e., fluctuation in instantaneous heart rate that results from autonomic influences on the sinus node) is a well-established measure of overall autonomic balance, and a validated marker of risk for adverse outcomes of other chronic conditions associated with autonomic dysfunction such as coronary disease and heart failure⁴¹. In particular, the high frequency (0.12-0.40 Hz) component of heart rate variability provides a reliable marker of *parasympathetic* autonomic activity, based on autonomic blockade studies showing that heart rate variability in the high frequency range is influenced by vagal but not sympathetic influences on the heart⁴²⁻⁴⁴. Measurements will be obtained at baseline and 12 weeks for visits at the [name] site only using a Biopac MP150 monitoring system (Santa Barbara, CA), according to protocols established by the North American Society of Pacing and Electrophysiology⁴⁵. Specifically, two electrocardiograph (ECG) electrodes will be attached to participants' torso/chest, and a 20-minute continuous ECG recording will then be taken with the participant in the seated position. Prior to measurement, women will be queried about any history of cardiac arrhythmias that could influence heart rate variability interpretation. To minimize diurnal variation, recordings will be obtained in the same 2-hour time of day at both visits. Women will sit in a quiet, ambient-temperature room, and will also be asked to abstain from tobacco or alcohol for 24 hours prior to recording. For 10 minutes during recording, they will also be asked to perform two computer-based stress tasks designed to assess vagal reactivity and sympathetic nervous system activity. Data will be analyzed using Mindware software (Gahanna, OH), which will calculate multiple time domain heart rate variability parameters (e.g., mean heart rate, standard deviation of N-N interval, square root of mean squared difference of successive N-N

intervals), as well as frequency domain heart rate variability parameters reflecting the distribution of heart rate variability over different frequencies (e.g., high frequency (0.12-0.40 Hz), low frequency (0.04-0.12 Hz), and low frequency/high frequency ratio).

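### The 12-week HRV/PEP recording is not timed relative to device use, so Aim 2 cannot separate a short-lived after-effect of slow breathing from sustained autonomic change

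*Combined protocol and SAP*

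**What the plan says.** **Recording conditions (D.5.2 A).** Women sit in a quiet room at ambient temperature. Clock time is fixed: "recordings will be obtained in the same 2-hour time of day at both visits". They "will also be asked to abstain from tobacco or alcohol for 24 hours prior to recording". D.5.2 B takes the impedance recording at the same time and adds no condition on prior device use.

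**Practice (D.4.2, D.4.3).** For the active arm: "Participants will be instructed to use RESPeRATE for at least 15 minutes per day for a total of 12 weeks". The control arm has the same daily minimum. Neither section makes an exception for visit days.

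**9-week reminder (D.6.7).** "They will be reminded to bring their completed voiding diary, their RESPeRATE device, and their actigraph and sleep diary with them". The timing of practice on the visit day is not mentioned.

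**12-week visit (D.6.8).** "Participants will return their third completed voiding diary, the RESPeRATE device, and the wrist actigraph and sleep diary". At the same visit, "Participants will also undergo repeat assessment of heart rate variability and impedance cardiography".

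**Baseline (D.6.4).** HRV and PEP are measured "at this visit (if they are randomized"), and the text places this after instruction on the assigned device.

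**Device log (D.4.2, D.4.3).** Both devices store "the time, date, and number of sessions in which it was used". D.7.2 and Appendix A have the log downloaded at 12 weeks.

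**Analysis (D.10.1, D.10.4).** Aim 2 compares resting HRV and PEP, then reactivity, by ANCOVA. The same autonomic change enters the structural equation model. Beyond adherence monitoring, the device data have one stated analytic use: cumulative minutes of effective practice against bladder outcomes.

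**The concern.** The authors accept that recent exposures can disturb these recordings, since they control tobacco, alcohol and time of day. The exposure under test, which the trial expects to act on the autonomic system, is not on that list. One woman may finish a session shortly before the recording and another may have practised the previous evening, and both comply with the protocol.

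If slow breathing leaves a short-lived shift in HRV or PEP, the 12-week contrast mixes that shift with whatever 12 weeks of practice has changed. Aim 2 reads the contrast as better autonomic control and then as a mechanism for the bladder effect. A result driven by a session earlier that day would support a narrower statement.

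**Working it through.** **1. Does another part of the design absorb it?**
- *Same 2-hour window:* fixes clock time, not time since the last session.
- *Control device:* D.4.3 says it balances sitting still, relaxing and wearing the belt. It does not balance slow breathing. Only the excess of paced breathing over relaxation is therefore unbalanced, but that excess is what matters here.
- *Baseline adjustment:* the run-in device does not pace breathing (D.6.3), so no home slow-breathing session precedes baseline and ANCOVA cannot remove an after-effect at 12 weeks. If active women try their assigned device before the baseline recording, baseline could also shift, with the opposite effect on measured change.
- *Off-treatment recording:* none. Autonomic measures are taken at baseline and 12 weeks only, and the 24-week contact is by mail (Appendix A).

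**2. Direction.** Pacing at 5–10 breaths/min corresponds to 5/60 = 0.083 Hz to 10/60 = 0.167 Hz. The high-frequency band in D.5.2 starts at 0.12 Hz, which is 0.12 × 60 = 7.2 breaths/min. A woman who still breathes more slowly than that during the recording could lose high-frequency power. D.5.2 describes no respiration measurement during the recording. The shift could go either way.

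**3. The plan's own precision for secondary outcomes (D.10.2).** Inputs: 80 per group, 15% loss, so 80 × 0.85 = 68; two-sided 5%; within-subject correlation ρ of 0.4–0.8.
- Unadjusted standard error for a unit SD: √(2/68) = 0.1715.
- Power at 0.5 SD: Φ(0.5/0.1715 − 1.96) = Φ(0.955) = 83%.
- Detectable difference at 80% power: 2.802 × 0.1715 = 0.48 SD. With ANCOVA, multiplying by √(1−ρ²) gives 0.44 SD (ρ = 0.4) to 0.29 SD (ρ = 0.8).

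The plan's 0.5 SD is consistent with this as a rounded, slightly conservative figure.

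**4. Illustration with assumed after-effects.** Let a share *p* of active women carry an after-effect of *a* SD beyond any in controls, with no sustained effect. The between-arm shift is *p·a*, and SE = √(1−ρ²)·√(2/68), which is 0.157 at ρ = 0.4 and 0.103 at ρ = 0.8. The two-sided rejection rate is Φ(*pa*/SE − 1.96) + Φ(−*pa*/SE − 1.96). Neither *p* nor *a* is in the documents.

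| Assumed *p*, *a* | Shift | ρ = 0.4 | ρ = 0.8 |
|---|---|---|---|
| none | 0 | 5% | 5% |
| 0.25, 0.2 SD | 0.05 SD | 6% | 8% |
| 0.50, 0.3 SD | 0.15 SD | 16% | 31% |
| 0.50, 0.5 SD | 0.25 SD | 36% | 68% |

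These rates are the same if the shift is negative. A negative shift could also hide a real effect: with a true 0.5 SD difference and ρ = 0.4, a shift of −0.15 SD takes power from Φ(0.5/0.157 − 1.96) = 89% to Φ(0.35/0.157 − 1.96) = 61%.

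The recordings are made at one site only, so 68 per group is an upper limit. At an assumed 34 per group, the 0.15 SD case gives 10–18%.

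**5. Mediation.** A uniform after-effect shifts the treatment-to-mediator path, and so the indirect effect whenever the mediator-to-outcome path is non-zero. An after-effect that varies between women can weaken the second path. It can also strengthen it, if the more adherent women both practise that day and improve more.

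**The case against.** **No after-effect is documented.** The documents give neither size nor duration. Sessions are done at home, and travel and other procedures in a visit of about two hours may intervene. This stands: the table is conditional, and its lowest case is close to the nominal 5%.

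**The on-treatment state may be the right target.** Aim 2 asks whether the intervention improves autonomic control, and the 12-week diary is also kept during daily practice. If repeated daily shifts are the mechanism, a recording near practice is not wrong. This partly stands. It is a reason to say which effect is meant, because the plan as written cannot tell the two apart.

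**Selecting on visit-day behaviour breaks randomisation.** Correct. Any analysis by time since last session can only be a sensitivity analysis.

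**External recording standards may cover this.** D.5.2 cites some, and they cannot be checked here.

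**Stronger readings that the documents do not support.** A reader might infer that the gap biases Aim 2 in favour of the active arm. The overlap of the pacing range with the 0.12 Hz limit rules out that certainty. A reader might also infer that the interval is never captured. The log holds session times in both arms; what is missing is any rule on timing and any use of those times for the autonomic outcomes. Nor can a definite fraction of the 0.5 SD detectable difference be attributed to after-effects, since both factors would be assumed.

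**Conclusion.** The gap is real and worth closing, chiefly because closing it is cheap. The plan neither sets the interval between device use and the 12-week HRV/PEP recording nor uses the logged session times when it analyses those outcomes. An after-effect specific to slow breathing would fall on the active arm and could not be told apart from sustained change, in the Aim 2 contrast or in the mediation model.

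Whether such an after-effect exists, how large it is and which way it points cannot be settled from the documents. On the assumed values and 68 per group, false-positive rates run from 6–8% to 36–68%. The calculation assumes a simple mean shift and ignores the small extra variance from mixing women with and without an after-effect. The point concerns secondary outcomes and an exploratory mediation analysis. The primary diary outcome is unaffected.

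**What to change.** 1. In D.5.2, D.6.4, D.6.8 and the 9-week reminder in D.6.7, state for both arms that the HRV/PEP recording is taken before any device use that day. Reconcile this with the daily-practice instruction in D.4.2 and D.4.3 and with the return of the device at the 12-week visit in D.6.8. How that day's practice is handled is for the investigators to decide.
2. Note the start time of each recording, derive hours since last session from the downloaded log, and report it by arm.
3. In D.10.1, pre-specify a sensitivity analysis of the Aim 2 contrast by that interval, labelled as sensitivity only because the interval arises after randomisation. The intention-to-treat ANCOVA stays the main analysis.
4. If timing is not controlled, word Aim 2 and its conclusions as not separating acute from sustained autonomic effects.

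Cost: a few lines of protocol and reminder text, one time entry and one derived variable. There is no change in sample size. The downside is a small scheduling constraint on the visit day, and some women will have practised beforehand anyway.
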